3. Contraindication to transfusion or history of prior reactions to transfusion blood products

INCUBATION PERIOD AND ONSET OF SYMPTOMS 3 DAYS AGO		FIRST WEEK				SECOND WEEK				LONG TERM INFO PENDING
		WARD Illness day 4	WARD Illness day 5	WARD Illness day 6	WARD Illness day 7	WARD/ICU Illness day 8	ICU Illness day 9	ICU Illness day 10	ICU Illness day 11	
Typical features according to current publications Age Mean (SD) 55.5 (13-1), Male (68%) Exposure to Huanan seafood market in Wuhan, China (49%) Chronic medical underlying illness (51%) Admission to Intensive Care Unit (23%)										
REPEATED SAMPLING OF THE NASOPHARYNX AND TRACHEAL ASPIRATES (IF INTUBATED) BY rRT-PCR FOR THE COVID-19		Initial important viral shedding		Decrease of the viral shedding sometimes associated with transient respiratory deterioration		Respiratory failure, increase of the viral shedding and viremia or Decrease of the viral shedding, and superinfections		Duration of viral excretion unknown		
OXYGEN THERAPY AND MECHANICAL VENTILATION		NO		Consider oxygen support	FNC	FNC followed by MV	MV		MV	
ORGAN FAILURE		Typical signs according to current publications Fever, cough, and shortness of breath (15%) bilateral pneumonia (75%), lymphopenia (35%), thrombocytopenia (12%), prothrombin time decreased (30%), elevated liver enzyme levels (about 30%)		Deterioration of respiratory status with most often spontaneous recovery		ARDS If shock beware of superinfections ⚠️ Possible renal failure Neurological failure unlikely Hemostasis disorders		YES		
CO-INFECTION/SUPERINFECTION		NOT LIKELY				Consider a possible HAP/VAP and other nosocomial infections (see text for diagnostic procedures)		Profound immune paralysis and late onset infections		
ANTIBIOTICS		NO				Consider antibiotic therapy		YES		
ANTIVIRAL AGENTS		NO				Consider antiviral agents if deterioration ^a				

FNC = flow nasal cannula; HFNC = high flow nasal cannula; HAP = healthcare-associated pneumonia; VAP = ventilator-associated pneumonia; MV = Mechanical ventilation;
^a The use of immunomodulation including corticosteroids is unlikely but debated

Figure 1 (from Bouadma et al Int Care Med 2020) describes what is known about the potential patient course of COVID-19 pneumonia. Our goal is to intervene in the middle of “green” area and improve patient status and avoid ICU admission.

LIST OF ABBREVIATIONS

ADR: Adverse Drug Reaction
ADE: Antibody-mediated enhancement of infection
AE: Adverse Event/Adverse Experience

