5.3 Study population

Inclusion Criteria for Enrollment

1. Patients must be 18 years of age or older
2. Hospitalized with COVID-19 respiratory symptoms and confirmation via COVID-19 SARS-CoV-2 RT-PCR testing. Patient is willing and able to provide written informed consent and comply with all protocol requirements.
3. Patient agrees to storage of specimens for future testing.
4. If female must not be pregnant and/or breastfeeding.

Exclusion Criteria

1. Female subjects with positive pregnancy test, breastfeeding, or planning to become pregnant/breastfeed during the study period
2. Receipt of pooled immunoglobulin in past 30 days
3. Contraindication to transfusion or history of prior reactions to transfusion blood products

Table: Schedule of Events

Study period	Screen	Baseline	Transfusion	Follow-up				
Day	-1 to 0	0	0	1	3	7	14	28 ⁴
Eligibility								
Informed consent	x							
Demographic and Medical history	x							
COVID-19 symptom screen	x							
SARS-CoV-2 RT-PCR for eligibility	x							
Pregnancy test	x							
ABO ₃	x							
Study Drug Administration								
Randomization		x						
Drug infusion			X					
Study Procedures								
Vital signs	x	x	XXXX ⁴	x	x	x	x	
Physical examination	x		x	x		x		
Symptom screen	x	x	x	x	x	x	x	x
Concomitant medications	x	x	x					
Assessment with 7-point ordinal scale		x		x	x	x	x	x
Adverse event monitoring		x	x	x	x	x	x	x
Laboratory testing								
CBC and CMP		x		x		x	x	
SARS-CoV-2 RT-PCR ⁵		x			x	x	x	
SARS-CoV-2 antibody		x		x	x	x	x	
Blood for future testing		x		x	x	x	x	

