6.2 Concomitant medications will be documented on the CRF

- Prescription medications
- Over the counter medications
- Herbal treatments/nutritional supplements
- Blood products

7. Statistical considerations

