2. Study Plasma Administration: 1-2 units of plasma will be transfused. Time at start and end of infusion will be recorded and Vital signs will be measured immediately prior to infusion, 10-20 minutes after start of infusion, at completion of infusion and 30-60 minutes after the end of the infusion
3. COVID-19 symptom screen (fevers, cough, shortness of breath)
4. Assessment of clinical status (7-point ordinal scale)
5. New medical conditions, concomitant medication, AE evaluation
6. physical examination
7. COVID-19 testing (RT-PCR) from nasopharyngeal, throat and stool (optional) samples
8. Blood typing, CBC, comprehensive metabolic panel, C-reactive protein
9. Serological testing: anti-SARS CoV-2 titers
10. Stored samples for future studies (cytokines, CD4-CD8, HLA-DR)

Day 1-7 (or for duration of hospitalization)

1. Vital signs daily
2. COVID-19 symptom screen (fevers, cough, shortness of breath)
3. Assessment of clinical status (7-point ordinal scale)
4. New medical conditions, AE evaluation
5. physical examination
6. CBC, comprehensive metabolic panel, CRP daily
7. Serological testing: anti-SARS CoV-2 titers
8. Stored samples for future studies

Day 28:

Key issues to consider f/u by phone, alive, at home, in hospital (ICU or not), on supplemental O2 or not, back to work, fully, partially, SNF, nursing home, LTAC0

1. COVID-19 symptom screen (fevers, cough, shortness of breath)
2. Assessment of clinical status (7-point ordinal scale)
3. New medical conditions, AE evaluation

Day 60 and 90:

1. COVID-19 symptom screen (fevers, cough, shortness of breath)
2. Assessment of clinical status (7-point ordinal scale)
3. New medical conditions, AE evaluation

10. Efficacy, virology and PK measures

Clinical Efficacy (ordinal scale)

1. Death/Cardio-circulatory arrest at anytime
2. Transfer to ICU
3. Type and duration of respiratory support (and other ICU support)in ICU
4. ICU mortality and LOS
5. Hospital mortality and LOS
6. Ventilator-free days
7. 28 day mortality

Virologic measures

1. Rates, levels and duration of SARS-CoV-2 RNA in NP swabs by RT-PCR at days 0, 3, 7 and 14. Other specimen types may be tested as available (eg., BAL fluid, tracheal secretions, sputum, etc.) or when RT-PCR assays are validated for additional sources (i.e., stool, blood).

2. Serologic positivity and neutralization antibody titers for anti-SARS-CoV-2 at days 0, 1, 3, 7 and 14 (additional days 21 and 28 may be included, as available).

11. Risks and benefits

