- 1 = Mild: Transient or mild discomfort (<48 hours); no medical intervention/therapy required.)
- 2 = Moderate: Some worsening of symptoms but no or minimal medical intervention/therapy required)
- 3 = Severe: Escalation of medical intervention/therapy required
- 4 = Life-threatening: Marked escalation of medical intervention/therapy required.
- 5= Death

Assessment of Association

The association assessment categories that will be used for this study are:

- Associated – The event is temporally related to the administration of the study product and no other etiology explains the event.
- Not Associated – The event is temporally independent of the study product and/or the event appears to be explained by another etiology.

The investigator must provide an assessment of association or relationship of AEs to the study product based on:

- Temporal relationship of the event to the administration of study product;
- Whether an alternative etiology has been identified;
- Biological plausibility;
- Existing therapy and/or concomitant medications.

13. Safety Oversight

Monitoring Plan

1. All AE and SAW will be reviewed by protocol team in real time.
2. A medical monitor will be appointed by the sponsor for safety oversight of the clinical study.
3. A data safety monitoring board (DSMB), led by **[name]** composed of independent experts without conflict of interests will be established. The Board will review the study before initiation and at least yearly thereafter. The Board will review study data to evaluate the safety, efficacy, study progress, and conduct of the study
4. An Independent Safety Monitor (ISM) will be appointed. The ISM is a physician with expertise in infectious diseases and whose primary responsibility is to provide timely independent safety monitoring. An ISM is in close proximity to the study site and has the authority to readily access study participant records. The ISM reviews any SAE that occurs at the study site in real time and provides a written assessment.

Study monitoring

1. As per ICH-GCP 5.18 and FDA 21 CFR 312.50, clinical protocols are required to be adequately monitored by the study sponsor. Monitors will verify that
 - a. There is documentation of the informed consent process and signed informed consent documents for each subject
 - b. There is compliance with recording requirements for data points
 - c. All SAEs are reported as required
 - d. Individual subjects' study records and source documents align

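### Concomitant treatment is scheduled for recording only through the day of transfusion, although section 6.2 sets no end date and adverse-event causality needs it afterwards

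*Protocol*

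**What the plan says.** Three places in the protocol govern the recording of co-treatment.

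- **Schedule of Events (section 5.3).** The row reads "Concomitant medications x x x". The ticks fall under screening, baseline and transfusion; days 1, 3, 7, 14 and 28 are blank. A footnote to the table repeats the day 28 assessments at days 60 and 90.
- **Section 9, Study procedures.** Day 0, item 5 is "New medical conditions, concomitant medication, AE evaluation". The lists for Day 1-7, Day 28 and Days 60 and 90 carry "New medical conditions, AE evaluation" instead. There is no separate Day 14 list.
- **Section 6.2.** "Concomitant medications will be documented on the CRF", with four types named, one of them "Blood products". No start or end of collection is given.

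Two other places bear on the point. Under Assessment of Association (section 12), the investigator's causality judgement must take account of "Existing therapy and/or concomitant medications", and adverse events are documented from first administration until the subject completes or leaves the study. In Figure 1 of the Protocol Summary, the entries for antibiotics and antivirals are negative for the first week of illness and change in the second; the antiviral entry is "Consider antiviral agents if deterioration".

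**The concern.** The visit schedule stops asking about co-treatment just before the period in which the trial measures its endpoints and in which other treatment is most likely to start. A site that follows the schedule and section 9 to the letter enters nothing after Day 0; a site that follows section 6.2 might go on. The database could then be incomplete, and unevenly so from patient to patient.

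The trial is open label, so the treating team may manage the arms differently. If one arm receives more antivirals or other active treatment, part of any difference in ICU admission, ventilator-free days or mortality belongs to that treatment and not to the plasma. On the safety side, one serious adverse event judged associated with study product triggers a halt and review. Grade 3 is itself defined by escalation of therapy, and Grade 3 or higher events are compared between arms by Fisher's exact test. A by-arm table of co-treatment is the ordinary way to show whether such comparisons are fair, and the plan as scheduled would not supply the data for it.

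**Working it through.** The protocol states no figure to reproduce here. The check compares the passages, does one piece of date arithmetic and adds an illustration.

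**1. Count of scheduled entries after transfusion.**

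| Item | Days 1, 3, 7, 14, 28 | Days 60, 90 (repeat of day 28) |
|---|---|---|
| Adverse event monitoring | 5 of 5 | 2 of 2 |
| Concomitant medications | 0 of 5 | 0 of 2 |

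The total for concomitant medication is 0 of 7. Section 9 drops the item independently of the table, so the blank cells are not a fault in how the table was read.

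**2. Timing of likely co-treatment.** Inputs: entry between illness day 3 and 7 (section 9, determination of eligibility), and illness day 8 as the first second-week column of Figure 1.

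Study day = 8 − illness day at transfusion.

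- Entered on illness day 3: 8 − 3 = study day 5.
- Entered on illness day 7: 8 − 7 = study day 1.

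This takes the illness day as counted on the day of transfusion. If it is counted at a screening visit the day before, each value falls by one, giving study day 0 to 4. The eligibility item also allows entry within 72 hours of admission as an alternative; a patient who enters that way after illness day 7 falls outside this arithmetic.

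**3. What one patient weighs.** 20 subjects at 1:1 is 10 per arm, so one patient is 1/10 = 10 percentage points of an arm's rate.

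**4. Illustration of imbalance.** The documents give no co-treatment rate, so common rates p of 20% to 70% are assumed. With A and B the numbers co-treated in each arm, independent Binomial(10, p):

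P(|A − B| ≥ 3) = sum over |a − b| ≥ 3 of C(10,a) p^a (1−p)^(10−a) × C(10,b) p^b (1−p)^(10−b)

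| Assumed p | P(difference of 3 or more patients) |
|---|---|
| 20% | 0.157 |
| 30% | 0.220 |
| 50% | 0.263 |
| 70% | 0.220 |

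Chance alone gives a gap of at least 3 patients in about 16% to 26% of trials of this size, before any effect of open-label care. This shows that a visible imbalance is plausible. It does not measure any effect on an endpoint.

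**The case against.** The strongest reply is that the information is not lost. Section 6.2 is open-ended and names blood products, and the CRF itself is not shown. Section 16 makes the medical record the primary source document, requires it to hold the treatments given, and allows data to be abstracted from it. Corticosteroids appear among the outcome measures in the Protocol Summary, next to vasopressors, renal support and ECMO. Causality is judged by an on-site investigator, and the independent safety monitor can read the participant's records; neither depends on the CRF. All of this stands. A reader might infer that co-treatment after Day 0 would go unseen or could not be detected; the documents do not support that. The gap is in scheduled, systematic capture.

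Two other stronger readings also fail. A reader might take Figure 1 to place immunomodulation after transfusion as expected treatment, but its footnote calls that use unlikely though debated. A reader might also infer crossover of control patients to convalescent plasma outside the trial. No passage mentions it. That none forbids it after randomization is a reason to record antibody products, and is no evidence that crossover will happen.

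Finally, treatment begun after transfer to ICU cannot have caused or prevented that transfer. This is right, and it limits the concern for ICU admission to treatment given beforehand. Ventilator-free days, mortality and adverse events remain exposed to treatment at either time, and start dates are what would separate the two.

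What the reply does not remove is the conflict between an open-ended rule and a schedule that ends at Day 0. No passage schedules abstraction of general co-treatment after that day.

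**Conclusion.** The point holds as an inconsistency in the collection window. Concomitant medication is scheduled at 0 of 7 time points after transfusion, against a CRF rule without an end date and a causality assessment that needs the information throughout follow-up. By the protocol's own disease course, antibiotics and antivirals come under consideration at about study day 1 to 5, on the assumption that illness day is counted at transfusion.

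The consequence is that unequal co-treatment would not be systematically available for a by-arm report. Its direction and size cannot be stated, because the documents give no co-treatment rate. With 10 per arm, recording would support description and not reliable adjustment. This is a worthwhile and cheap correction; it does not invalidate the design.

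**What to change.** Reconcile the Schedule of Events and section 9 with section 6.2:

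- Extend the concomitant medications row to days 1, 3, 7, 14 and 28, and add the item to the Day 1-7 and Day 28 lists in section 9. Section 9 has no Day 14 list, so the table row governs that visit unless a list is added.
- State in section 6.2 when collection starts and ends. Because the table footnote repeats day 28 assessments at days 60 and 90, say whether the item carries over to those contacts.
- Record, with start dates, antivirals, immunomodulators including corticosteroids, antibiotics, and any blood or antibody product, abstracted from the medical record.
- Report these by arm. Leave the randomised comparison unchanged.

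The cost is a little more chart abstraction and data entry for 20 subjects, from a record that is already the source document.
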